[name], Prof of Paediatrics and Consultant Neonatologist, Cork University Maternity Hospital [name], Senior Lecturer and Consultant Pediatrician, Department of Pediatrics and Child Health and INFANT, UCC Cork University Hospital

Protocol/Sponsor Number: GB02/17UCC Principal Investigator: [name]

1 Background

It is well known that sleep is essential for brain development (3) and learning (4). Infants require extensive sleep for development of the hippocampus, pons, brainstem, and midbrain and for optimizing physical growth. It is also essential for *brain plasticity*; the genetically determined ability of the infant brain to change its structure and function in response to the environment. Studies in young animals have shown that sleep deprivation leads to increased programmed cell death, smaller brain size, and loss of brain plasticity, all of which have negative long-term impact on behaviour and learning ability (5-7).

Infant massage, a form of systematic tactile stimulation by human hands, improves sleep hygiene. Very little is known about how massage influences early brain development but it is certainly linked to the theory of environmental enrichment, which has been well established in animal models. (8-10).

2 Aims of the BabySMART project

The aim of this project is to optimise the infant's sensory experience through a multi-sensory enrichment programme, including massage (a massage utilising a scented lotion before sleep each day), to encourage more structured sleep and ultimately show improved developmental and cognitive outcomes.

3 Hypothesis

The BabySMART study will examine the effect of a structured sensory enrichment programme including massage, delivered by parents according to a structured programme following training, on both the quality and quantity of sleep and on subsequent neurodevelopment

4 Significance of the question

It is well known that sleep is essential for brain development and maturation. Studies have shown that sleep-deprived young animals have smaller brains with loss of brain plasticity, which leads to diminished learning and adverse long-term behavioural effects. It is also established that infant massage improves sleep hygiene and is linked to the theory of environmental enrichment, which promotes brain development. Brain development during the first years of life depends on the quality of stimulation in the infant's environment. Early child development is a life-long determinant of health and well-being. There are significant societal and economic benefits from optimal infant cognitive development (2).

Protocol/Sponsor Number: GB02/17UCC Principal Investigator: [name]

5 Trial Objectives and Purpose

Primary objective

To assess the effect of a structured sensory enrichment programme on Infant sleep using qualitative and quantitate measures.

Secondary objective

To assess the effect of a structured sensory enrichment programme on neuro-development as assessed by a standardised neurodevelopmental assessment at approx. 4 months and approx. 18 months of age.

6 Description of protocol methodology

6.1 Type of Trial

We will undertake a multi-centre, unblinded, randomised, controlled study to evaluate whether a multi-sensory enrichment programme in the first 4 months of life will improve sleep architecture and neurodevelopment in healthy infants.

We do not interpret this study as a clinical trial, as defined by the Control of Clinical Trials Act, 1987 and 1990.

6.2 Subjects

A total of 200 full term healthy infants will be studied. Recruitment will take place at CUMH and UCL-ICH London.

Inclusion criteria for participant selection are:

- Infants born > 37 weeks gestation
- Single births
- Not requiring admission to the Neonatal Unit
- Healthy infants without suspected congenital or metabolic anomalies

Exclusion criteria for participant selection are:

[figure not shown]
- Infants born < 37 weeks gestation
- Multiple births

Page 6

• Severe metabolic or genetic anomaly that would require ongoing specialist care in the infancy period.

Admission to the Neonatal Unit.6.2.1 Figure 1 Flow chart design of study

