6.3 Contact with study participants

Mothers will be approached post- delivery, at the bedside, usually within 48 hours, in the wards in CUMH, they will be informed about the study and given a study leaflet to read. If they decide to participate in the study the consent form will be signed and the next steps will be explained to the parents.

BabySMART Protocol Version 2.0 20 JUL 2017

Protocol/Sponsor Number: GB02/17UCC Principal Investigator: [name]

Once the day of consent assessment is complete, ideally day 2 after birth, parents will be informed that the next appointment will be in approximately 2 - 3 weeks and that a member of the BabySMART team will contact them to schedule this appointment and randomisation will occur at this follow up visit.

Phone Call for follow on appointments in BabySMART

- 1. All postnatal appointments are to be made 1-2 weeks prior to scheduled follow-up.
- 2. Remind mothers of the BabySMART study; ask how baby has been getting on.
- 3. Schedule an appointment for follow up appointment in the INFANT research centre in the CUH (approx. 4 months and approx. 18 months).
- 4. Again, tell them we will send a reminder text the day before and if there are any problems to contact the study team and that an alternative appointment can be made.

Reminder texts

For the approx. 2 week, 4 month and 18 month visit texts

A reminder of your appointment with the BabySMART Study tomorrow in the INFANT Research Centre in CUH. Thanks from BabySMART

7 List of BabySMART Procedures

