7.1 Anthropometry (2 weeks, 4 month and 18 month time points)

Weight, height (supine length) and head circumference will be measured using a standard technique and equipment at the visits that will take place at approximately 2 weeks, 4 months and 18 months. Measurements will be taken according to the relevant INFANT Work Instructions. The same measuring equipment will be used for the duration of the study and staff will be both familiar with the technique and equipment before completing a measurement.

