7.2 EEG measurements (4 month time points)

A sleep video/ EEG will be performed on babies recruited into the BabySMART study at approximately 4 months of age (conceptual). Parents will be invited to bring their child to the baby sleep lab, INFANT Research Centre in the CUH for this appointment. The timing of this should be coordinated so the recording commences following a feed around the time of the baby's longest daytime nap. The recording will last for the duration of the baby's sleep.

Recording parameters

The EEG recording will be made using the study EEG machine and follow the INFANT Sleep EEG Work Instructions which were devised according to the American Academy of Sleep Medicine (AASM) (10). Each recording will be made using disposable electrodes and will include respiration, Electrooculography (EOG), Electrocardiography (ECG) and Electromyography (EMG) measurements for qualification of sleep states.

EOG is a technique for measuring/ recording eye movements. Pairs of electrodes are typically placed either above and below the eye or to the left and right of the eye and the recorded potential is a measure of the eye's position.

ECG is the process of recording the electrical activity of the heart over a period of time using electrodes placed on the skin. These electrodes detect the tiny electrical changes on the skin that arise during each heartbeat from the heart muscle. These electrodes will be placed on the left and right deltoid muscle of the arm.

EMG is used to measure muscle movement and two electrodes will be applied approximately 2 cm to the left of the midline and 2cm to the right of the midline, with both electrodes approx. 2cm below the inferior edge of the mandible.

A specialized respiration electrode will be used to measure respiration rate. All recordings will be assigned a study ID number and pseudo anonymised. Any incident findings will be followed-up clinically.

BabySMART Protocol Version 2.0 20 JUL 2017

Protocol/Sponsor Number: GB02/17UCC Principal Investigator: [name]

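### Does recruiting in London while writing every visit venue for Cork leave the plan in conflict with itself?

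*Combined protocol and SAP*

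**What the plan says.** Section 6.1 sets the design: "We will undertake a multi-centre, unblinded, randomised, controlled study". Section 6.2 gives a total of 200 infants and adds "Recruitment will take place at CUMH and UCL-ICH London"; section 7.3 repeats the total and that sentence. Section 8 assigns duties at each site, and section 11 foresees ethics review in each country.

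The operational text is written for Cork. In section 6.3, mothers are approached "at the bedside, usually within 48 hours, in the wards in CUMH". The phone-call instructions for the 4- and 18-month visits read "Schedule an appointment for follow up appointment in the INFANT research centre in the CUH". The reminder message for the 2-week, 4-month and 18-month visits reads "A reminder of your appointment with the BabySMART Study tomorrow in the INFANT Research Centre in CUH". For the sleep EEG, section 7.2 says "Parents will be invited to bring their child to the baby sleep lab, INFANT Research Centre in the CUH for this appointment". Section 7.3 places the massage training in the same Cork centre. Section 7.1.5 places the Griffiths assessment in CUH, with a home visit allowed where needed.

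No venue is stated outright for allocation. Section 6.3 says of the 2 to 3 week appointment that "randomisation will occur at this follow up visit".

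**The concern.** The plan names two recruiting centres and appears to describe the work of one. The ward approach is the sharpest case, since a mother who gives birth in London is not in a CUMH ward. Training delivers the intervention and the EEG records sleep, and neither has a written alternative to Cork. Allocation also seems to be in Cork, though only by inference, because it happens at a visit whose reminder message names CUH.

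Two things would be at stake. If London families had to travel, few might take part or stay, and the 200 infants would in effect be a Cork sample. If London ran the steps locally, rooms, staff and equipment would differ from the text, and the visible plan does not say how site enters randomisation or analysis. Section 13 adds weight, because it permits deviation only in emergencies and requires each one to be reported.

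**Working it through.** **Counting the venue statements.** The count covers statements that place a contact or procedure, leaving aside the two recruitment sentences.

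| Step | Section | Venue | Alternative written? |
|---|---|---|---|
| Approach to mothers | 6.3 | CUMH | No |
| 4- and 18-month appointments | 6.3 | CUH | No |
| Reminder for 2-week, 4- and 18-month visits | 6.3 | CUH | No |
| Sleep EEG, 4 months | 7.2 | CUH | No |
| Massage training, 2 weeks | 7.3 | CUH | No |
| Griffiths III, 4 and 18 months | 7.1.5 | CUH | Yes, home |

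Cork is named in 6 of 6, London in 0 of 6, and a home option is given in 1 of 6. The drop-in massage classes have no stated venue.

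**What the count can bear.** The two recruitment sentences also say where families are met. With them there are 6 + 2 = 8 statements, and London is named in 2 of 8. The six also overlap: the phone-call item and the reminder cover the same 4- and 18-month visits, and the EEG and Griffiths both fall at 4 months. The steps with a Cork venue and no alternative reduce to three: ward approach, 2-week training and 4-month EEG. The 18-month visit is tied to Cork only by the phone-call item and a template message. Its Griffiths assessment may be done at home, and sections 7.1 (anthropometry) and 7.4 (questionnaires) name no venue.

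**Equipment wording.** Section 7.1 says "The same measuring equipment will be used for the duration of the study". The natural reading is consistency over time, which two sites can each observe. The reference in section 7.2 to the study's EEG machine is ordinary phrasing. Neither conflicts with a second site.

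**Does any passage send London families to Cork?** No. The text fits equally well with a Cork sponsor that wrote out its own pathway and left London's to local documents. Apart from the ward sentence, the passages are incomplete and do not contradict one another.

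**Effect on the arm comparison.**

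- London runs the steps locally: infants at a site share that site's rooms and equipment whichever arm they are in. Site differences would mainly add variance or variation in effect between sites. Randomisation keeps them from biasing the comparison by themselves.
- London families must travel: those who cannot reach the 2 to 3 week visit leave before allocation, which cannot unbalance the arms. Loss after that visit would be ordinary dropout.

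**Effect on precision.** The plan states no alpha, power, target difference, standard deviation, allocation ratio or site split, so the 200 cannot be reproduced and no loss can be derived from it. A bound needs assumptions: 1:1 allocation, two-sided alpha 0.05, 80% power, a London share of 10% to 50%, and every London infant lost without replacement. The detectable difference in SD units is (1.960 + 0.842) × √(2/n), with n per arm:

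- 200 infants, n = 100: 2.802 × √(2/100) = 0.40
- 180 infants (20 lost), n = 90: 2.802 × √(2/90) = 0.42
- 100 infants (100 lost), n = 50: 2.802 × √(2/50) = 0.56

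The documents support neither the London share nor the total loss. The target of 200 is not divided by site, so Cork could recruit to the total. These figures are therefore not evidence of a shortfall.

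**The case for a change.** The strongest case for acting is that the ward sentence and the recruitment sentence cannot both be followed for a London mother, and that training and EEG are core steps with no London venue. Under section 13, doing them locally could look like a reportable deviation for each family. Other wording points the same way: the instructors hold an Irish massage qualification, the researcher follows HSE protocols, and the example questionnaire uses Irish school certificates, PRSI and euro income bands. The operational text was evidently drafted for Ireland.

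The mismatch in the ward sentence stands, and so does the absence of London venues from the visible text. The larger consequences do not. A reader can tell that two centres were intended, since five sections say or assume so; what is missing is logistics and the split between sites. Deleting London and the multi-centre label would be wrong if London recruits for procedures done in Cork or at home. Stratifying by site and adding a site covariate are reasonable preferences, but they would fill an unwritten analysis plan and would not correct a rule that the plan states. A venue mismatch does not require them.

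**Conclusion.** No change to the plan follows. London is named for recruitment, and the visible text gives no London venue for the approach and consent, the 2-week training or the 4-month EEG. Site staff would fill that gap sensibly with their own wards, rooms and equipment. Because recruiting site is known for each infant before allocation, analysts can report numbers by site and adjust for it if both sites contribute.

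The size is three procedures without a written London venue. No bias, loss of power, shortfall below 200 or effect on the conclusion has been shown, and none can be derived without a site split. With no primary endpoint named, the effect on the primary objective cannot be stated either; parent-reported sleep by app or diary does not depend on Cork.

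The conclusion rests on the visible text. Figure 1 and the INFANT Work Instructions are not shown and may already contain the London arrangements. It also assumes that, if London runs the steps, infants in both arms there are handled in the same local setting.

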6.3 Contact with study participants

Mothers will be approached post- delivery, at the bedside, usually within 48 hours, in the wards in CUMH, they will be informed about the study and given a study leaflet to read. If they decide to participate in the study the consent form will be signed and the next steps will be explained to the parents.

BabySMART Protocol Version 2.0 20 JUL 2017

Protocol/Sponsor Number: GB02/17UCC Principal Investigator: [name]

Once the day of consent assessment is complete, ideally day 2 after birth, parents will be informed that the next appointment will be in approximately 2 - 3 weeks and that a member of the BabySMART team will contact them to schedule this appointment and randomisation will occur at this follow up visit.

Phone Call for follow on appointments in BabySMART

- 1. All postnatal appointments are to be made 1-2 weeks prior to scheduled follow-up.
- 2. Remind mothers of the BabySMART study; ask how baby has been getting on.
- 3. Schedule an appointment for follow up appointment in the INFANT research centre in the CUH (approx. 4 months and approx. 18 months).
- 4. Again, tell them we will send a reminder text the day before and if there are any problems to contact the study team and that an alternative appointment can be made.

Reminder texts

For the approx. 2 week, 4 month and 18 month visit texts

A reminder of your appointment with the BabySMART Study tomorrow in the INFANT Research Centre in CUH. Thanks from BabySMART

7 List of BabySMART Procedures

7.1 Anthropometry (2 weeks, 4 month and 18 month time points)

Weight, height (supine length) and head circumference will be measured using a standard technique and equipment at the visits that will take place at approximately 2 weeks, 4 months and 18 months. Measurements will be taken according to the relevant INFANT Work Instructions. The same measuring equipment will be used for the duration of the study and staff will be both familiar with the technique and equipment before completing a measurement.

7.1.1 Trans-epidermal water loss measurement (TEWL) (2 day, and 4 month time points)

Trans-epidermal water loss (TEWL) measurement will be taken using standard technique and equipment (Delfin Vapometer) at the visits occurring on approximately Day 2 and 4 months. Parents will be asked not to apply emollients on the morning of the visit and any non-compliance will be documented. Three measures will be taken and the average reading recorded in the eCRF.

BabySMART Protocol Version 2.0 20 JUL 2017 Page 7

Protocol/Sponsor Number: GB02/17UCC Principal Investigator: [name]

Page 8

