7.3 Sensory enrichment programme including infant massage

A total of 200 full term healthy infants will be recruited. Recruitment will take place at CUMH and UCL-ICH London. Parents will be invited to provide proxy consent for their infant to participate and also for their own participation in the BabySMART study.

Once Day 2 screening assessment is complete, parents will be informed that the next appointment will be in approximately 2 - 3 weeks and that a member of the BabySMART team will contact them to schedule this appointment. Randomisation will occur at this visit. Participants will be randomised to either a structured sensory enrichment programme including infant massage (intervention arm) or to the control arm.

The massage will be applied according to IAIM (International Association of Infant Massage). Created in 1976 by Vimala McClure, it is the first global organisation with a professional programme which is run in several countries around the world, due to its proven benefits. The purpose of IAIM is to create a nurturing touch and communication through training, education and research so that parents, caregivers and children are loved, valued and respected throughout the world community.

At the 2 week visit parents will be provided with training in infant massage by an instructor who has completed a Baby Massage Ireland trainer course. The massage should be carried out daily until the 4 month visit. Massage training will be completed on-site in the INFANT Research Centre in the new Paediatric unit in the CUH and the JOHNSON'S® HEAD-TO-TOE® extra moisturizing baby cream will be supplied at these appointments

Mothers will be informed about the enrichment programme which will include the benefits of baby massage, infant cues, duration of application, points of care for application and application technique at this stage. The technique of massage application will be shown to the mother by the researcher using a model baby (doll).

Mothers will be asked to apply the massage on their own baby as instructed and they will be observed to determine whether they applied the massage correctly or not. Training will be reinforced both at the training session and by the provision of a training DVD which will be provided to parents.

Baby massage education will also be given at drop in classes where a review of the strokes will be undertaken. Each parent's application of baby massage will be observed and evaluated for correct

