BabySMART Protocol Version 2.0 20 JUL 2017 Page 9

Protocol/Sponsor Number: GB02/17UCC Principal Investigator: [name]

technique. Extra JOHNSON'S® HEAD-TO-TOE® extra moisturizing baby cream will be supplied at these classes. Parents will be encouraged to massage their babies a minimum of 3 x 15-minute sessions including a minimum of 2 of the 6 areas to be massaged, every day for the first 4 months of life.

The researcher will follow HSE protocols to help women improve the care of their baby, or other questions that may arise; sleep positions, weaning, vaccines, feeding, bathing.

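### The TEWL emollient rule covers only the morning of the visit, so cream applied shortly before an afternoon 4-month reading is allowed and unrecorded, probably more often in the massage arm

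*Combined protocol and SAP*

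**What the plan says.** Section 7.1.1 schedules TEWL "at the visits occurring on approximately Day 2 and 4 months". On preparation it says only: "Parents will be asked not to apply emollients on the morning of the visit and any non-compliance will be documented". On the measurement it says: "Three measures will be taken and the average reading recorded in the eCRF". It refers to standard technique and names the device. It gives no minimum time since the last emollient, no skin site, no clock time and no place in the order of the visit.

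Section 7.2 sets the hour of the 4-month sleep-lab appointment: "The timing of this should be coordinated so the recording commences following a feed around the time of the baby's longest daytime nap".

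Section 7.3 describes the intervention: "Parents will be encouraged to massage their babies a minimum of 3 x 15-minute sessions", and continues "including a minimum of 2 of the 6 areas to be massaged, every day for the first 4 months of life". It also states "The massage should be carried out daily until the 4 month visit", with no pause for the visit day. Moisturizing cream is supplied at the training appointments and again at the drop-in classes.

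The reminder text in Section 6.3 does not mention emollients. The 4-month questionnaire in the Appendix asks all parents how often they moisturise and with which product, but not when they last did so.

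**The concern.** The restriction shows that the protocol itself regards recent emollient as a problem for a TEWL reading. A rule that names the morning protects a morning reading. It does not, as written, protect one taken at 14:30. Cream applied after midday is not barred, so it is not non-compliance and would not be documented under Section 7.1.1.

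This would matter little if recent cream were equally common in both arms. But one arm is asked to massage several times a day, is given cream for it, and is told to continue until the visit at which TEWL is read. Section 7.3 asks nothing comparable of controls. A gap in the rule is therefore likely to act more on one arm than on the other. A 4-month difference could then be read as an effect of the programme on the skin when part of it is cream still on the skin.

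**Working it through.** The plan gives no TEWL mean, SD, target difference or planned comparison, so there is no figure to reproduce. The check has three steps.

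**1. What the literal rule permits.** The clock times here are assumptions.
- Visit at 10:00, last cream at 20:00 the evening before: 14 h from cream to reading, compliant.
- Visit at 14:30, last cream at 12:30: 2 h from cream to reading, also compliant.

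Both families follow the rule, and under Section 7.1.1 their records look the same.

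**2. How often a session could fall in the unprotected window.** Assume three sessions spread evenly over 12 to 14 waking hours. The spacing is 12/3 = 4 h to 14/3 = 4.67 h. The window runs from noon to the reading.
- Reading at 13:00: window 1 h, so 1/4.67 = 21% to 1/4 = 25% of such infants have a session in it.
- Reading at 14:30: window 2.5 h, so 2.5/4.67 = 54% to 2.5/4 = 63%.
- Reading before noon: 0%.

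These shares apply only to intervention infants read after noon, a proportion the documents do not give. They also assume that every session uses cream. A further reduction applies because only 2 of the 6 areas need be covered and the measured site is not stated.

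**3. What a given imbalance would do to the comparison.** Assumptions: 100 infants per arm (the protocol states 200 in total and no allocation ratio), no true effect, a constant shift in creamed readings, unchanged variance, and a two-sided 5% normal test.
- SE of the difference = √(2/100) = 0.141 SD.
- Bias b = (excess share of creamed readings in the intervention arm) × (shift in SD).
- Rejection rate = Φ(b/SE − 1.96) + Φ(−b/SE − 1.96).

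| Excess share | Shift 0.25 SD | Shift 0.5 SD | Shift 1.0 SD |
|---|---|---|---|
| 0% | 5.0% | 5.0% | 5.0% |
| 10% | 5.4% | 6.4% | 10.9% |
| 25% | 7.3% | 14.3% | 42.4% |
| 50% | 14.3% | 42.4% | 94.2% |

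Worked cell: 25% × 0.5 SD = 0.125 SD; 0.125/0.141 = 0.88; Φ(−1.08) + Φ(−2.84) ≈ 0.143.

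The excess share means the difference between arms, so equal use of cream in both arms puts the trial in the top row. The documents fix neither the share nor the shift, so the table shows only how the result depends on them. It does not estimate the bias in this trial.

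**The case against.** The case against is substantial, and much of it stands.

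- **Afternoon readings are inferred.** Section 7.2 times the start of the EEG recording, not arrival and not TEWL. Electrodes go on first, so a midday nap may mean a morning arrival. That TEWL is taken at the same appointment is the natural reading of Section 6.3, but it is not stated. The sponsor may also mean the rule to cover all the time up to the visit. If so, the text should say so, since families and staff could apply it differently.
- **The measured site may not be creamed.** No site is given and only 2 of the 6 areas are required.
- **The imbalance is not proven.** Section 15 says the products go to participating parents without limiting them to one arm, and controls may moisturise on their own account.
- **The massage frequency is not uniform in the text.** Section 2 describes massage before sleep each day, and Section 7.3 has both a daily massage and at least three sessions a day. These statements need to be reconciled.
- **TEWL is in neither stated objective.** No skin-barrier hypothesis is given.

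Three stronger readings are tempting, and the documents do not support them. A reader might infer that every intervention infant with an afternoon visit is read on creamed skin. Step 2 shows that this does not follow even when three sessions a day are assumed, and the share of afternoon visits is not stated. A reader might also infer that the interval can never be recovered. The MiChild app or paper diary (Section 7.5) captures adherence to the programme in real time and may show some visit-day sessions, although the app is optional and no field for last emollient use is described. Finally, a reader might conclude that TEWL cannot support any statement about the skin. The documents give neither the size nor the duration of the effect of cream on a reading, so that is not shown.

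None of this closes the gap. As written, the rule permits recent cream before an afternoon reading and asks for no record of it, in a trial where cream is supplied for the massage assigned to one arm.

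**Conclusion.** The concern holds in limited form. A 4-month arm difference in TEWL could partly reflect recent cream. This requires that some readings are taken after midday, that the measured site was creamed, and that recent cream is more common in one arm. The last condition is likely given the massage instruction, but it is not established. The size is unknown. On the assumptions above, the false-positive rate runs from 5% with no imbalance to 94.2% at the most extreme combination tried, and nothing in the documents places the trial within that range.

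The reach is narrow. Day 2 TEWL precedes randomisation at the 2 to 3 week visit, so it cannot differ by arm for this reason. The sleep and neurodevelopment conclusions do not depend on TEWL. This is an inexpensive improvement to an ancillary measurement and not a threat to the trial's main results.

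**What to change.** 1. In Section 7.1.1, replace the reference to the morning with a restriction that runs until the TEWL reading has been taken, whatever the hour, with the same wording in both arms. The sponsor should set when it starts.
2. Reconcile that restriction with the daily-massage instruction in Section 7.3 for the day of the 4-month visit.
3. Add a line on the restriction to the reminder text in Section 6.3.
4. State that TEWL is taken before electrode placement.
5. Record the time of last emollient use and the measured site in the eCRF for every infant, not only for those who break the rule.
6. Repeat the 4-month TEWL comparison excluding infants with emollient use inside the interval. Because exclusion depends on behaviour after randomisation, report it beside the comparison of all infants and not in its place.

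The cost is a revised sentence and a line on order in Section 7.1.1, a visit-day clarification in Section 7.3, a line in the reminder, two eCRF fields, one extra analysis and the amendment procedure in Section 12. The downside is that some families hold the cream for a few more hours on one day. If only one element is adopted, recording the time of last use in both arms is the most valuable, because it allows the problem to be checked in the data.
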